## **Participants and recruitment**

Participants: We will recruit 120 current ENDS users defined as using ENDS either daily or occasionally in the past 30 days (as in Vargas-Rivera et al., 2020). Individuals who report smoking cigarettes or other tobacco/nicotine products will be included to increase the generalizability of results and enhance recruitment provided that they don't use these tobacco products >5 times/past month (as in Ben Taleb et al., 2020). As our study focuses on nicotine dependence related parameters, any substantial use of other tobacco/nicotine products will likely bias our planned assessments. Similarly, the pre-study 12 hours abstinence period from all tobacco/nicotine products and using the same product type/brand ensures that study outcomes reflect mainly each session's condition. We aim to recruit equal numbers of men and women.

Inclusion and exclusion criteria: Participants need to be generally healthy, between 21-35 years old, provide written informed consent, and agree to attend the lab on two occasions and use their ENDS product according to the study protocol. Participants will be asked to abstain from

ENDS and all tobacco/nicotine products use for at least 12 hours prior to each session. The abstinence period is needed to clear nicotine from prior-to-study use and ensure that all study measures are influenced mostly by the study conditions. Testing short-term abstinence of ENDS, which does not produce carbon monoxide (CO) is an ongoing challenge (Hiler et al., 2017). Therefore, we will follow published recommendations (Blank et al., 2016) to use the gold standard of plasma nicotine to eliminate data from non-compliant participants later. Because this will entail a loss of data, we will try to minimize that and improve compliance by asking the participants to arrive at the scheduled study sessions one hour early for an observation period, and complete a CO test (Blank et al., 2016). The CO test will be good to detect combustible tobacco products' use (e.g. cigarette smoking), and act as a bogus pipeline for ENDS use (Blank et al., 2016). This procedure has been shown to cut participants' non-adherence to the abstinence condition to <10% (Spindle et al., 2018), which is consistent with our own experience (Vargas-Rivera et al., 2020). A blood draw will be completed before each session, abstinence will be confirmed using plasma nicotine levels less than 5 ng/ml (Benowitz, Hukkanen, & Jacob, 2009).

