Individuals with a self-reported history of chronic disease, psychiatric conditions, history of cardiovascular disease, low or high blood pressure (BP) (systolic BP>150 mm Hg, or diastolic BP>100 mm Hg), seizures, or regular use of prescription medications (other than vitamins or birth control) will be excluded (St Helen et al., 2017). This will be assessed by history and physical examination conducted by the research nurse during a screening visit. The research nurse will have access to an on-call Medical Monitor (physician) in case of concern or for consultation at any point during the study (as is the current practice in our lab). The physical examination will include measuring BP, heart rate (HR), temperature, pulse oximetry, and weight/height. Importantly, considering the current COVID-19 pandemic we will follow CDC and FDA guidelines for clinical research and COVID-19 to minimize any potential risk of infection transmission as detailed in our Human Subject Protection part (CDC, 2020b; FDA, 2020c).

Briefly, we will apply a protocol consisting of 5 main areas;

- 1- Screening of Participants for COVID-19;
- 2- Social and Physical Distancing;
- 3- Use of Personal Protective Equipment (PPE);
- 4- Cleaning and disinfecting;
- 5- Personal Hygiene and Hand Washing.

Participants with symptoms/history suggestive of COVID-19 (e.g.  $\geq 100.4^{\circ}\text{F}$ , cough, contact) or with a history of cannabis use (risk for e-cigarette or vaping product use-associated lung injury-EVALI) will be excluded from participation (details in Human Subjects Protection). As knowledge about COVID-19 is rapidly evolving we will apply best practices at the time of study to protect human

subjects and our staff (e.g. require vaccination record if such becomes feasible). FIU has started providing vaccination to all research staff with direct contact with human subjects, and free-of-charge COVID-19 testing facilities have become available within and in the vicinity of FIU (e.g. FIU-Curative., 2020). Women will be excluded if they are breast-feeding or test positive for pregnancy (by urine pregnancy testing) at screening (St Helen et al., 2017). Finally, we will also exclude individuals if they intend to quit e-cigarette within the next 3 month and if they use THC in e-cigarette.

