Screening, and informed consent: Individuals who are identified as potentially eligible based on the phone screening will be asked to attend an onsite-screening, which will involve assessment of inclusion/exclusion criteria, physical examination, COVID-19 screening, and urine pregnancy testing for women. Prior to screening, potential participants will undergo a review of the study and consent procedures to ensure that they understand the study, its risks/benefits, and their rights as research participants. Consented (written) individuals will then undergo a physical examination conducted by the research nurse, who will have access to an on-call Medical Monitor (physician) in case of concern or for consultation at any point of the study as it is the standard practice in our lab. Successfully consented participants will be scheduled for their 1st session and asked to abstain from all tobacco/nicotine use 12 hours prior to it.

Sample size. All power calculations were performed with PASS19 (PASS, 2019). We built our calculation of the sample size for this study based on our preliminary study of the effect of NR on subjective (e.g. craving, urges) and puff topography measures (pls. see Preliminary Studies), where medium effect size (Cohen's  $f=0.2$ ) depending on nicotine condition was detected. Expecting a maximum 20% loss due to noncompliance with abstinence or study protocol (Vargas-Rivera et al., 2020), this study will include a dropout inflated sample of 150 ENDS users. Using repeated measures ANOVA F-test with 2 within and 1 between factors, a total dropout adjusted sample size of 120 (2X60) participants will have at least 80% power to detect small to medium-size effect (Cohen's  $f=0.1-0.2$ ) or larger for 2 within-subject (NR condition and time) and 1 between subject (use frequency) factors, as well as their interactions at 0.05 level of significance, assuming sphericity and a moderate correlation (0.5) among repeated measures (Cohen, 1988).

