Experimental protocol. Participants from each frequency group will be randomly assigned to one of the nicotine concentration conditions and attend the lab for two, ~2-h sessions, separated by a 48-h washout period, and differ by nicotine concentration (3%,5%) or (0%, 5%). Session order will be counterbalanced to mitigate order and carry-over effects. At the beginning of the 1st session, participants will provide consent, complete demographic and personal information including age, sex, socioeconomic status, race/ethnicity, and detailed tobacco/nicotine use history. Participants will get familiarized with the study procedures, measures, and they will be given time to adapt to the lab. After adaptation, continuous measurement of physiological responses begins, and 10 ml of venous blood is sampled, lung function tests will be conducted, and participants are asked to respond to subjective measures (pls. see below Outcome Measures). Participants will inhale on their session ENDS ad libitum for up to 60 minutes (as in Vargas-Rivera et al., 2020). At the end of the ENDS use period 10 ml of blood will be sampled, lung function tests repeated, and subjective measures assessed. The session will terminate 30 minutes after the last puff, and the 2nd session is scheduled. A follow-up phone call at 3-month post-study will be made to evaluate nicotine preferences and changes in ENDS and tobacco use.

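### Pregnancy is tested only at screening, with no limit on the gap to session 1 and no test on the day of ENDS use

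*Combined protocol and SAP*

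**What the plan says.** All of the following is in the combined protocol and SAP, under Participants and recruitment unless stated otherwise.

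- **Exclusion rule** (Inclusion and exclusion criteria): "Women will be excluded if they are breast-feeding or test positive for pregnancy (by urine pregnancy testing) at screening".
- **When the test is done** (Screening, and informed consent): the onsite screening visit includes "physical examination, COVID-19 screening, and urine pregnancy testing for women".
- **What follows screening** (same paragraph): "Successfully consented participants will be scheduled for their 1st session", with 12 hours of abstinence beforehand. No maximum interval is given. The Recruitment paragraph also counts the screening visit separately from the two lab sessions.
- **Session day** (Inclusion and exclusion criteria; Experimental protocol): participants come an hour early for observation and a CO test. Physiological monitoring, a blood draw, lung function tests and questionnaires follow. Then: "Participants will inhale on their session ENDS ad libitum for up to 60 minutes". The stated use of the blood sample is plasma nicotine.
- **Second session** (Experimental protocol): the sessions are "separated by a 48-h washout period", and "The session will terminate 30 minutes after the last puff, and the 2nd session is scheduled". No upper limit is stated.
- **Numbers**: "We aim to recruit equal numbers of men and women" (opening paragraph), and "this study will include a dropout inflated sample of 150 ENDS users" (Sample size).

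Table 2 and the Protection of human subjects section mention no pregnancy test. Birth control appears only as a permitted medication, and nothing in the text provided requires contraception or asks participants to report a new pregnancy.

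**The concern.** The sponsor has decided that pregnant women should not take part, although everyone eligible already uses ENDS. A negative urine test supports that decision only for the day it is taken. A woman may conceive after screening, or may have been too early in pregnancy at screening for the test to detect it. Because the gap to session 1 has no limit, the plan can be followed exactly and still give a pregnant woman a study-supplied device for up to 60 minutes per session.

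Under Study Design, part 1 compares 5% with 3% nicotine and part 2 compares 5% with 0%, so every participant has a 5% session. The eligible age range is 21 to 35, and occasional users are admitted. For them, an hour of unrestricted use at 5% may exceed usual intake.

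The stake is participant safety. Nothing here biases a treatment comparison or changes power.

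**Working it through.** **1. Is there a test anywhere after screening?**

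| Place in the document | Checks before ENDS use | Pregnancy test? |
|---|---|---|
| Screening, and informed consent | Eligibility, physical examination, COVID-19 screening, urine test | Yes |
| Inclusion and exclusion criteria (session arrival) | One-hour observation, CO test, blood draw for nicotine | No |
| Experimental protocol (in session) | Monitoring, blood draw, lung function, questionnaires | No |
| Table 2 | Study measures by time point | No |
| Protection of human subjects | Approval, training, consent | No |

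The Experimental protocol also places consent at the start of session 1, which might suggest that screening and session 1 are one visit. They are not: the Recruitment paragraph counts them separately, and the abstinence instruction given after screening implies a gap of at least 12 hours.

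**2. How many women?**

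The plan's enrolment figure reproduces: 120 / (1 − 0.20) = 150. With equal numbers of men and women, 150 × 0.5 = 75 women would attend session 1.

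**3. How many pregnancies would a session 1 test newly detect?**

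The documents give neither a conception rate nor a screening-to-session interval, so both are assumed: 0.5% to 2% conceiving per month, and a gap of one or four weeks. If the urine test has the same detection lag at both visits, the pregnancies that are newly detectable at session 1 are those conceived in a window as long as the gap, so the lag cancels.

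Expected number = women × monthly rate × gap in days / 30.4

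| Gap | 0.5% per month | 2% per month |
|---|---|---|
| 7 days | 75 × 0.005 × 7/30.4 = 0.09 | 75 × 0.02 × 7/30.4 = 0.35 |
| 28 days | 75 × 0.005 × 28/30.4 = 0.35 | 75 × 0.02 × 28/30.4 = 1.4 |

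**4. Cross-check on lower assumed rates.**

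With an annual rate r and a gap of w weeks, the expected number is 75 × [1 − (1 − r)^(w/52)].

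| Annual rate | 1 week | 4 weeks | 12 weeks |
|---|---|---|---|
| 2% | 0.03 | 0.12 | 0.35 |
| 5% | 0.07 | 0.30 | 0.88 |
| 10% | 0.15 | 0.61 | 1.80 |

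At 5% a year and four weeks, the chance of at least one such pregnancy in the study is about 26%.

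**5. Reading the figures.** Both sets point to a small count, probably below one or two in the whole study. They are upper bounds on the exposures a repeat test would avert, since a woman who already knows she is pregnant may say so.

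**6. Session 2.** At the planned 48-hour spacing the window is two days: 75 × 0.02 × 2/30.4 = 0.10 even at the higher monthly rate. A second repeat therefore adds little unless session 2 is delayed, which the text allows.

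**The case against.** The strongest reply is that little is at risk. Participants already use ENDS, anyone planning to quit within three months is excluded, and each session follows 12 hours without nicotine. For a regular user the session largely replaces her own vaping, and in part 2 one of the two sessions contains no nicotine. The upper figure of 1.4 needs both a four-week gap and 2% conceiving per month, which is about 21% a year (1 − 0.98^12). Across most of the range the repeat test would find nobody. This stands as a limit on the size of the concern. It does not remove it, because the sponsor made pregnancy disqualifying in this same population of users.

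A second reply is that the criterion is worded as a positive test at screening, so the plan is consistent with itself and a session-day check is a stricter standard. The wording does read that way. But the purpose of the exclusion is to keep pregnant women from study exposure, and a single undated test serves that purpose less well as the gap lengthens.

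A third reply is that silence proves little. The Experimental protocol paragraph omits the CO test that the eligibility section requires, and Table 2 omits lung function. A study guide is still to be written, and the consent pages are not available for review. This is fair: a repeat test, or an instruction to report pregnancy, may exist elsewhere. The conclusion is therefore confined to the protocol text, which sets out session-day checks in two places and names no pregnancy test in either. Access to a research nurse and on-call physician, and ethics approval, are useful but do not amount to a test before exposure.

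**Conclusion.** The concern holds. The text provided specifies one pregnancy test, at screening; it sets no limit on the time to session 1; and it lists no test on the day of use. Following the plan can expose a woman with a detectable pregnancy to a 5% nicotine session.

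The size is modest: about 0.09 to 1.4 newly detectable pregnancies at session 1 among 75 women, for gaps of one to four weeks. This rests on an assumed conception rate, an assumed interval, equal detection lag at both visits, and an even split of men and women among 150 enrolled. The added exposure per woman is also limited. This is a participant-safety gap that should be closed because closing it costs almost nothing. It has no bearing on the validity of the estimates.

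**What to change.** Add one step to the Experimental protocol: repeat the urine pregnancy test during the one-hour observation period before session 1, before any ENDS use, and exclude on a positive result. Repeat it at session 2 only when that session falls more than a few days after session 1 instead of at about 48 hours.

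The cost is about 75 × 1 = 75 tests of a kind already in use, and at most 75 × 2 = 150 if every second session runs late. They fit in time already scheduled, with no extra visit and no change to the sample size or analysis. The downside is an occasional withdrawal, which the plan absorbs because recruitment continues until 120 participants have complete sessions. If the lab already tests on the day, one sentence saying so is enough.

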## **Study Design**

This study is divided into 2 parts (studies), whereby the first part will be 2X2 comparing NJOY 5% and 3% to test the effects of partial nicotine reduction, and the second part will be using the NIDA Standardized Research Electronic Cigarette (SREC) for Clinical Research 5% and 0% (placebo), to test the effect of the total reduction using the same pods and juices from the same manufacturer.

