Recruitment: We will recruit participants using a combination of online, offline, and in-person recruitment methods to ensure successful recruitment (Buller et al., 2012). Offline items such as posters, flyers, and study inserts will be posted and distributed on FIU and other university campuses in Miami (e.g. University of Miami), nearby off-campus locations, and around ENDS shops in Miami. Online recruitment will include student listservs, Facebook, and other social media. In-person recruitment will involve handing out flyers and word-of-mouth targeting vape shops in Miami. Recruitment materials will be Institutional Review Board (IRB) approved and will have contact information (phone, e-mail) for initial eligibility screening. Based on previous experience, we expect to study 10 subjects/month (Vargas-Rivera et al., 2020). We will continue recruitment until we reach the target sample (120 with complete sessions). While recruitment is

always a challenge, [name]'s lab has easily recruited JUUL users in the past year with negligible drop out for 2 session protocol using comparable incentives, to the extent that we had to turn down many eligible participants due to sampling saturation (Vargas- Rivera et al., 2020). This is due to the widespread use of ENDS, and JUUL among young adults, especially in a large university with about 57,000 students such as FIU, where our lab is located. Participants completing the on-site screening and 2 lab sessions, and 3-month phone follow-up will be compensated a total \$200 at the end of the study to encourage completeness.

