## **AIM 1: To assess the subjective and clinical effects of nicotine reduction on ENDS users.**

Objective and hypothesis. This aim will help understand users' response to NR and how it will influence their product satisfaction, nicotine dependence, intention to quit or use in the future, lung functions, and clinical symptoms. We hypothesize that NR will be associated with less satisfaction, withdrawal suppression, and intention to use in the future and that such an effect will be more pronounced in total compared to partial NR and in high compared to low-frequency users.

Outcomes. We will utilize our clinical lab model to study the effect of NR on the following outcomes assessed according to the plan described in Table 2. All assessments will be based on instruments that are standard in clinical lab studies of addictive behaviors modified for the ENDS we plan to use (Vargas-Rivera et al., 2020). Participants will use a tablet to respond to these measures using RedCap.

**Outcomes.** We will utilize our clinical lab model to study the effect of NR on the following outcomes assessed according to the plan described in Table 2. All assessments will be based on instruments that are standard in clinical lab studies of addictive behaviors modified for the ENDS we plan to use (Vargas-Rivera et al., 2020). Participants will use a tablet to respond to these measures using RedCap. Briefly, we will assess;

1. Demographic and baseline characteristics; including age, race, sex, and reasons for ENDS use. Other characteristics will include the frequency of ENDS use, and the history of other tobacco/nicotine products use (Amato, Boyle & Levy, 2016; Zavala-Arciniega et al., 2019; Vargas-Rivera et al., 2020).
2. Dependence measures including; 1) *Use satisfaction* (Modified Cigarette Evaluation Questionnaire (mCEQ) (Arger et al., 2017); 2) *Dependence* (Questionnaire of Smoking Urges-brief and the Minnesota Nicotine Withdrawal Scale, Penn State Electronic Cigarette Dependence Index (Ben Taleb et al., 2018; Foulds et al., 2015; St Helen et al., 2017); 3) *Puff sensory effects* (Duke Sensory Scale, (Malson & Pickworth, 2002)).

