Intention to quit or use in the future	X		X	X
Nicotine preference, changes in ENDS use				X
Reasons for ENDS use	X			
Puff topography (puff volume/ml, duration/sec; inter-puff interval/sec)		X		
Cardiovascular measures (BP; HR; oximetry)		X		
Plasma nicotine (ng/ml)	X		X	
Nicotine (playback)			X	
Aldehydes (playback)			X	

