## **AIM 2: To assess the puffing behavior in response to nicotine reduction.**

**Objective and hypothesis.** This aim will help understand users' compensatory puffing behavior in response to NR and its effect on plasma nicotine as the main substance sustaining addiction to ENDS. *We hypothesize that NR-related compensatory puffing will be more pronounced in high vs. low-frequency users.*

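### The claimed 80% power counts all 120 participants in one nicotine contrast, but each contrast rests on only one of two parts, about 60 people

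*Combined protocol and SAP*

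**What the plan says.** The Sample size paragraph (Participants and recruitment) plans a repeated measures ANOVA with two within-subject factors, nicotine condition and time, and one between-subject factor, use frequency. It states that "a total dropout adjusted sample size of 120 (2X60) participants will have at least 80% power to detect small to medium-size effect", defined as Cohen's f of 0.1 to 0.2 or larger. The claim covers all three factors "as well as their interactions at 0.05 level of significance, assuming sphericity and a moderate correlation (0.5) among repeated measures". The planning effect is f = 0.2 for nicotine condition, from a preliminary study. Allowing for 20% loss, 120 becomes 150.

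Other sections fix what the 120 are:

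- **Recruitment:** "We will continue recruitment until we reach the target sample (120 with complete sessions". So 120 is the whole study.
- **Aim 3, aerosol generation:** 240 topography sessions, which is 120 × 2.
- **Study Design:** two parts, described as separate studies. One compares NJOY 5% with 3%; the other compares the NIDA research e-cigarette at 5% with 0%.
- **Experimental protocol:** people in each frequency group are randomised to one nicotine pair and attend two sessions.
- **Statistical analysis:** the primary ANOVA has nicotine at two levels, one pair or the other, and time. It has no term for part and no pooled model.

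The hypotheses include interactions. Aim 1 expects that "such an effect will be more pronounced in total compared to partial NR and in high compared to low-frequency users". Aim 2 states: "We hypothesize that NR-related compensatory puffing will be more pronounced in high vs. low-frequency users".

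**The concern.** The powered model has one nicotine factor and no term for part, so it describes 120 people contributing to a single nicotine contrast. The rest of the document does not run that design: each contrast uses only the people assigned to that pair.

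The calculation also appears to assume four measurements per person (two sessions, pre and post). Table 2 shows that topography is recorded only during use, and that satisfaction, the visual analogue scale and the sensory scale are recorded only afterwards. The Statistical analysis section averages topography to one value per participant and condition. These outcomes therefore have two measurements per person.

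This paragraph is the only justification of size for all three aims. A null result within a part on an effect near f = 0.1 could be taken as coming from a test with at least 80% power. The Aim 2 frequency-by-nicotine hypothesis on topography is such a case, and its power at f = 0.1 is about a third.

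**Working it through.** **Inputs from the Sample size paragraph:** N = 120, α = 0.05, correlation ρ = 0.5, sphericity, f = 0.1 to 0.2, 20% loss. **Measurements per person (m), from Table 2 and the Statistical analysis section:** 4 for pre/post outcomes, 2 for once-per-session outcomes. **Assumed, because no allocation is stated:** 60 completers per part, 30 per frequency group.

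**Method.** Noncentral F test with 1 numerator and N − 2 denominator degrees of freedom (N − 4 for part-by-nicotine).

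- Within-subject terms and their interactions: λ = N m f² / (1 − ρ)
- Use-frequency main effect: λ = N m f² / (1 + (m − 1)ρ)

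**Step 1: the plan's own figures.** Inflation: 120 / (1 − 0.2) = 150, as stated. With all 120 in one contrast and m = 4:

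- Within terms, f = 0.1: λ = 120 × 4 × 0.01 / 0.5 = 9.6, power 0.87 (80% is reached at f = 0.091).
- Use frequency, f = 0.2: λ = 120 × 4 × 0.04 / 2.5 = 7.68, power 0.785 (80% is reached at f = 0.204).

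So the range 0.1 to 0.2 roughly reproduces, the lower end for within terms and the upper end for use frequency, but only under those two conditions. With all 120 and m = 2, within terms at f = 0.1 already fall to λ = 4.8, power 0.58.

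**Step 2: one part, N = 60.**

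| Term | m | λ at f = 0.1 | Power | λ at f = 0.2 | Power | f for 80% |
|---|---|---|---|---|---|---|
| Nicotine, time, interactions | 4 | 4.8 | 0.58 | 19.2 | 0.99 | 0.130 |
| Nicotine, frequency-by-nicotine | 2 | 2.4 | 0.33 | 9.6 | 0.86 | 0.184 |
| Use frequency | 4 | 0.96 | 0.16 | 3.84 | 0.49 | 0.291 |
| Use frequency | 2 | 0.8 | 0.14 | 3.2 | 0.42 | 0.319 |

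Simulation with 20,000 runs per setting agrees. For m = 2 it gives 0.330 (nicotine) and 0.333 (frequency-by-nicotine) at f = 0.1, and 0.864 and 0.859 at f = 0.2. For m = 4 both are 0.579 at f = 0.1. Use frequency at f = 0.2 gives 0.486 (m = 4) and 0.419 (m = 2).

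**Step 3: sensitivity to the split, within terms.**

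| Completers in the part | f = 0.1, m = 4 | f = 0.1, m = 2 | f = 0.2, m = 2 |
|---|---|---|---|
| 50 | 0.50 | 0.28 | 0.79 |
| 60 | 0.58 | 0.33 | 0.86 |
| 70 | 0.65 | 0.38 | 0.91 |

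**Step 4: what all 120 could support.** A part-by-nicotine test of total against partial reduction would have 0.87 (m = 4) or 0.58 (m = 2) at f = 0.1, and above 0.99 or 0.99 at f = 0.2. It reaches 80% at f = 0.091 or 0.129, where f is that of the interaction. Use frequency pooled over both parts would have 0.785 or 0.71 at f = 0.2. The plan specifies neither pooled analysis.

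**The case against.** The best defence is that 0.1 to 0.2 is a range across kinds of effect, not a promise of 80% at 0.1 for every test. Step 1 supports that reading, and at 60 per part nicotine and its interactions still reach 80% inside the range, at 0.13 or 0.184. The design effect is also the pilot 0.2, not 0.1. Both points stand, and they limit the problem to an overstated claim. They do not rescue it: use frequency is named as a powered factor, and within a part it needs f of about 0.29 to 0.32, beyond the top of the range. The pilot value is for nicotine condition; the documents give none for the frequency-by-nicotine interaction.

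A second defence is that separate analysis and the equal split are inferred. The 2X60 could mean parts or frequency groups, and the total-versus-partial hypothesis needs data from both parts. But if it means parts, there are 60 per part. If it means frequency groups, the Experimental protocol divides each group again. Pooling would average two different contrasts on two products, and once-per-session outcomes would still have only 0.58 at f = 0.1.

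It is also fair to say that the split is not the whole cause: the number of measurements matters too. In addition, the primary ANOVA as written omits use frequency, so the frequency figures concern tests that the Sample size paragraph and the hypotheses name but the primary model does not. Finally, the use-frequency main effect has no hypothesis of its own, which makes its shortfall less serious.

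**Conclusion.** The power statement is wrong as written and should be corrected. At 60 per part, power for nicotine and its interactions at f = 0.1 is 58% (pre/post) or 33% (once per session), against the stated 80% or more. The use-frequency main effect misses 80% throughout the stated range. The nicotine contrast keeps 86% to 99% at the pilot f = 0.2, so the study is not undersized for its main comparison at that effect.

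These figures rest on separate analysis of the parts, which is how the Study Design and Statistical analysis sections read, on an assumed equal split, and on the plan's own ρ of 0.5. Unequal allocation would make the smaller part worse. With 50 in a part, once-per-session power for nicotine at f = 0.2 drops just below 80%.

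**What to change.** Keep the sample. In the Sample size paragraph, replace the claim of at least 80% power at f = 0.1 to 0.2 with:

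> Assuming 60 completers per part, split equally by use frequency, a correlation of 0.5 and α = 0.05, each part has 80% power for f ≥ 0.13 (nicotine, time and interactions; pre/post outcomes), f ≥ 0.19 (nicotine and frequency-by-nicotine; outcomes measured once per session), and f ≥ 0.30 (pre/post) or f ≥ 0.32 (once per session) for the use-frequency main effect. At the pilot f of 0.2 the nicotine effect has 86% to 99% power per part.

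State the planned allocation between parts and frequency groups, and recompute if it is not equal.

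If a part-by-nicotine test across all 120 is added to the Statistical analysis section, add that it has 80% power for f ≥ 0.10 (pre/post) or f ≥ 0.13 (once per session). Note there that part and product are confounded. If the test is not added, leave that sentence out.

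The cost is wording only, apart from the optional test, which changes the analysis plan. No participants are added. The stated detectable effects become less favourable.
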